## 10. Statistical Analysis:

**Aim 1: To study the impact of 8 weeks of riluzole treatment on CNS glutamate concentrations in breast cancer patients with increased fatigue and high inflammation.**

**Hypothesis 1:** Breast cancer patients administered riluzole will exhibit greater decreases in basal ganglia and dACC glutamate compared to women treated with placebo.

Mixed-effects models for repeated measures (MMRM) will be employed to examine effects of group, time and their interaction on left and right basal ganglia glutamate or dACC controlling for baseline glutamate concentrations in separate analyses for each brain region. Relevant covariates including age, sex, race (white/non-white) and body mass index (BMI), socioeconomic status (as measured by household income), educational status, tumor stage, tumor receptor status (where appropriate), timing (adjuvant versus neoadjuvant) of chemotherapy and radiation (yes/no) will be sequentially tested in the models for goodness of fit (Akaike Information Criterion) and included as appropriate.

**Aim 2: To determine whether decreased CNS glutamate correlates with improved symptoms of fatigue and cognition dysfunction.**

**Hypothesis 2:** Decreased glutamate in the basal ganglia will be associated with decreased fatigue and improved motivation and processing speed. Decreased glutamate in the dACC will be associated with improved executive function and memory performance.

Random intercept linear mixed models will be used to assess whether change in left or right basal ganglia or dACC glutamate predict change in fatigue scores or change in neurocognitive function over time. Models will be adjusted for relevant clinical covariates (including IDS-SR, PSQI, BAI) as indicated above. Separate analyses will be run for each behavioral outcome (MFI, PROMIS) as well tests of cognition (HVLT-R, TMT PASAT COWAT RT FTT, RTT, and DSST) and motivation (DDT, EEfRT, Subjective Value Task, Effort and Delay Task, Daily Assessment/Mobile App Task, Gamble Task, and Go No-Go Variant Task.). Type I errors as a result of multiple testing will be controlled by using a step down Bonferroni procedure.[68]

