Thus, CNS glutamate may serve as a final common pathway to CNS pathology and behavioral and cognitive disturbances in breast cancer patients after treatment. Interestingly, memantine, a drug that antagonizes glutamate signaling was found to preserve cognition in cancer patients undergoing whole brain radiotherapy, indicating that blocking glutamate may have neuroprotective effects under conditions of an increased inflammatory load. Taken together, these data suggest that glutamate may be an outstanding target for reversing the behavioral pathology associated with inflammation during breast cancer and its treatment. Demonstration that targeting glutamate to reverse fatigue and cognitive changes in patients with high inflammation and could potentially help treat the long-term toxicities of breast cancer and its treatment. The goal of the current proposal is to test the hypothesis that reduction of glutamate in breast cancer survivors with fatigue and high inflammation will be associated with decreased CNS glutamate and decreased symptoms of fatigue and cognitive function including anhedonia and psychomotor slowing. To test these hypotheses the following aims are proposed:

**Aim 1: To study the impact of 8 weeks of riluzole treatment on CNS glutamate concentrations in breast cancer patients with increased fatigue and high inflammation.**

Using a double-blind randomized controlled trial design, 40 female breast cancer patients with increased fatigue ( $\geq 4$  on a 10 point scale) and high inflammation (CRP $>3$ mg/L) will be treated for 8 weeks with either riluzole or placebo (n=20 per group). At baseline and at 1 and 8 weeks of treatment, all subjects will undergo single voxel MRS to measure CNS glutamate. Voxels will be placed in the right and left basal ganglia and the dACC. In addition, chemical shift MRS imaging will be employed to explore potential glutamate changes in other brain regions of interest.

**Hypothesis 1:** Breast cancer patients administered riluzole will exhibit greater decreases in basal ganglia and dACC glutamate compared to women treated with placebo.

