## 11. Power Analysis:

A power analysis was conducted using our preliminary data examining a cohort of 50 unmedicated patients with major depression.[27] The study sample size was powered on the basis of Aim 1, which represents the primary hypothesis of the study that riluzole will decrease basal ganglia glutamate. Given a sample size of 40, an alpha of 0.05, a power of 0.80, we will be able to detect an effect size of Cohen's  $d=0.5$  which falls in the moderate range (computed using G\*power). This effect size is well within the range of the effect size ( $d$ ) of the differences in basal ganglia glutamate concentrations between high (CRP>3mg/L) and low (CRP<1mg/L) inflammation, which are expected in this study.

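### Aim 1 selects covariates by AIC on the trial outcome, so a nominal 5% group or Week-8 test runs at about 6-9% if group is in the model during selection; the deciding side and effect are also not named

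*Combined protocol and SAP*

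**What the plan says.** **Covariate rule.** The Aim 1 paragraph of Section 10 plans a repeated-measures mixed model (MMRM) to "examine effects of group, time and their interaction on left and right basal ganglia glutamate or dACC controlling for baseline glutamate concentrations", with one model per region. It then lists age, sex, race, BMI, socioeconomic status, education, tumor stage, receptor status, chemotherapy timing and radiation, which "will be sequentially tested in the models for goodness of fit (Akaike Information Criterion) and included as appropriate". The list is introduced as open. No order, direction or final set is fixed. Nothing says that selection is done blinded or without the group term.

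**Deciding test.** The Aim 1 title reads "To study the impact of 8 weeks of riluzole treatment on CNS glutamate concentrations". Section 11 sizes the trial on Aim 1, "which represents the primary hypothesis of the study that riluzole will decrease basal ganglia glutamate", and starts from: "Given a sample size of 40, an alpha of 0.05, a power of 0.80". Hypothesis 1 in Section 5 is wider: women given riluzole "will exhibit greater decreases in basal ganglia and dACC glutamate compared to women treated with placebo". Section 5 also says "Voxels will be placed in the right and left basal ganglia and the dACC", whereas the single-voxel acquisition text in Section 6 specifies two voxels only, left and right basal ganglia.

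**Multiplicity.** "Type I errors as a result of multiple testing will be controlled by using a step down Bonferroni procedure" is the last sentence of the Aim 2 paragraph. It does not define its family of tests.

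**The concern.** AIC selection on the outcome is a data-dependent step that the final p-value ignores. If group is left out, the covariate set is chosen without reference to assignment, so randomization still justifies the test, as it would for a fixed set. If group is in the model, the chosen set depends on assignment, and chance imbalances that sharpen the group term are more likely to be kept. With 40 women and about nine candidates, that is enough to move the error rate of the trial's one powered hypothesis. A step-down Bonferroni adjustment does not remove this, because the p-values it receives are already too small.

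The second gap compounds the first. Three effects are listed (group, time and their interaction), two basal ganglia sides are modeled separately, and no combination is named as deciding. The same data could be read as positive or negative for Aim 1.

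**Working it through.** **Inputs from the documents.** 40 women, 20 per arm, 1:1 allocation in blocks of 4 without stratification, alpha 0.05, MRS at baseline, Week 1 and Week 8, and ten listed covariates. All participants are women, so sex is constant: 10 - 1 = 9 usable candidates.

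**Assumptions not in the documents.** Normal errors, independent covariates, one column per covariate, complete data, correlation 0.5 between visits (0.7 as a variant), two-sided tests.

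**Selection threshold.** One extra column lowers AIC when twice the log-likelihood gain exceeds 2. Under the null, P(chi-square with 1 df > 2) = 0.157, so a useless covariate enters about 16% of the time, and 9 x 0.157 = 1.4 of nine enter on average. In simulated Week-8 ANCOVA at N = 40, sequential selection kept 1.6-1.7.

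**The plan's own level.** The MMRM simulation used two post-baseline visits, unstructured covariance, covariates as main effects, sequential AIC and 10,000 null runs (Monte Carlo SE about 0.25 points). With a fixed covariate set (none or all) it gives 5.0-5.6%, so the nominal 5% is essentially reproduced.

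**With AIC selection**, rejection rates under no drug effect:

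| Setting | Group in: Week-8 / group | Group out: Week-8 / group |
|---|---|---|
| 9 candidates | 7.0% / 7.9% | 5.3% / 5.2% |
| 5 candidates | 6.3% / 6.8% | 5.2% / 5.1% |
| 12 candidates | 7.5% / 8.9% | 4.9% / 5.1% |
| 9, correlation 0.7 | 6.4% / 6.6% | 4.9% / 4.3% |
| 9, about half binary | 6.8% / 7.4% | 5.0% / 4.8% |
| 9, three truly prognostic | 6.8% / 8.0% | 4.7% / 5.0% |

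**Cross-checks, group in.** A Week-8 ANCOVA at N = 40 under four forms of AIC selection gives 6.5-8.6% with 5-9 candidates and 8.0-10.2% with 12 columns. At N = 32 with nine candidates (40 x 0.8, reading the unit-less drop-out figure in Section 6 as 20%) the ceiling is 9.8%. A separate two-visit model with compound symmetry gives 6.0-8.8%.

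**Interaction test.** With complete data, covariate main effects cancel in the Week 8 minus Week 1 difference, so the group-by-time test stays at 4.9-5.4%. If covariate-by-visit terms are selected with group in, two simulations give 7.1% and 7.3%. In the second, the rate was 5.5% both with no covariates and with group left out.

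**What each effect tests.** Baseline is a covariate, so the responses are Weeks 1 and 8 only. With d = 0.5 and correlation 0.5, residual variance after baseline is 1 - 0.5^2 = 0.75 and the between-visit covariance is 0.5 - 0.25 = 0.25. The variance factor for 20 per arm is 2/20 = 0.1.

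- Week-8 contrast: SE = sqrt(0.75 x 0.1) = 0.274
- Group effect (visit average): variance (0.75 + 0.75 + 0.50)/4 = 0.50; SE = sqrt(0.05) = 0.224
- Interaction (visit difference): variance 0.75 + 0.75 - 0.50 = 1.00; SE = sqrt(0.10) = 0.316

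| True effect | Week-8 | Group | Interaction |
|---|---|---|---|
| Equal at Weeks 1 and 8: effect/SE | 0.5/0.274 = 1.83 | 0.5/0.224 = 2.24 | 0 |
| Power (noncentral t) | 43% | 59% | 5% |
| Week 8 only: effect/SE | 1.83 | 0.25/0.224 = 1.12 | 0.5/0.316 = 1.58 |
| Power | 43% | 19% | 34% |

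The interaction has no power beyond its 5% level for an effect already present at Week 1 and maintained. The background section cites glutamate change within one week of riluzole, so that pattern is plausible here.

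The power statement in Section 11 (d = 0.5 at 80% power) does not reproduce as a two-sample t test: 20 per arm gives 34% two-sided. That is a separate matter, and nothing here depends on it.

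**The case against.** The strongest defense is that the 6-9% needs two readings that the text does not settle: that group is in the model while covariates are tried, and that the group or Week-8 effect decides. The excess is then 1-4 points in a 40-woman trial meant to provide first mechanistic data. This stands as a limit on size and certainty. It does not remove the problem, because the models that the section describes contain group and nothing says it is taken out.

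The reply that the interaction test is unaffected stands only for main-effect covariates, which the section does not specify.

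It is also fair that the plan is not silent on priority. Section 11 makes basal ganglia glutamate primary, the Aim 1 title points to 8 weeks, and the step-down Bonferroni sentence is worded generally enough to cover Aim 1. A reader might infer that either basal ganglia side can count without correction, which would put error at about 12-13%. The documents do not support that: the figure requires the Bonferroni sentence to exclude Aim 1, and it rests on assumed correlations between regions. A reader might also infer that side and effect will be picked after the data are seen; the documents say nothing about timing. What remains is that left, right or mean, and the deciding effect, are not stated anywhere.

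**Conclusion.** The concern holds in conditional form. With group in the model during AIC selection, a single pre-named group or Week-8 test has type I error of about 6-9% instead of 5%, and up to about 10% with more covariate columns or fewer patients. These figures assume normal errors, independent covariates and complete data. The rate is about 5% if group is left out. For the group-by-time test it is about 5% with main-effect covariates and about 7% with selected covariate-by-visit terms. It would be too strong to say that the plan as written must exceed 5%, since selection without group is not excluded.

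Separately, the deciding side and effect are missing, and Hypothesis 1 and Section 11 disagree on whether dACC belongs to the primary claim. The choice of effect matters: power for an effect equal at both visits ranges from 5% to 59% under the stated assumptions. Both gaps affect the trial's primary hypothesis and should be closed before unblinding.

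**What to change.** **Covariates.** Replace AIC selection with baseline glutamate plus a short fixed set named before unblinding. Drop sex. Give women without chemotherapy, whom Section 6 admits, their own category, because an adjuvant-versus-neoadjuvant variable has no place for them. Put the other covariates in a sensitivity analysis. If selection is kept, state that it is done with group left out and before unblinding.

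**Deciding test.** Name the Week-8 riluzole-placebo contrast in basal ganglia glutamate from the MMRM, and state that it is tested at two-sided 0.05. It matches the Aim 1 title, and its power does not depend on what happens at Week 1. Say whether the outcome is left, right or the left-right mean. The mean would depart from the one-model-per-region plan and needs a rule for when one side is unusable, for example on spectral quality. State that dACC is tested after basal ganglia, or jointly by Holm, and that this rule governs Aim 1. Report Week 1 and each side as secondary.

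**Acquisition.** Reconcile Sections 5 and 6 on whether a dACC single voxel is acquired.

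**Cost.** Mostly protocol and SAP wording. The dACC reconciliation may reach the scan protocol. The downside is that a one-side-only or dACC-only result could no longer be claimed as primary success.

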### **Description of Study Procedures (Baseline 1, Startle Study, Baseline 2 and Weeks 1-8)**

All eligible participants with a CRP>3mg/L and a Fatigue Score  $\geq 4$  will complete Baseline 1, be randomized to receive riluzole (100 mg/d) or placebo at Baseline 2, and proceed to study visits at Weeks 1, 2, 4, and 8.

During the Baseline 1 visit and on Week 1 and Week 8, subjects will undergo magnetic resonance spectroscopy (MRS). Between baseline 1 visit and baseline 2 visit, participants will have the option of undergoing a parallel Startle Test Study protocol. This protocol will consist of either 1 or 2 visits, for completing psychiatric assessments and self-report forms and for completing a psychophysiological startle task. A schedule of all assessments is provided in Table 1. Approximately 30 mL of blood will be drawn at the same time of day between 8-10AM (to reduce potential circadian effects) under sterile conditions at Baseline 1 and 2 and Weeks 1, 4 and 8. Screening/safety labs are not time dependent. Safety labs will be completed at Baseline 2, Week 4 and Week 8. At each visit, self-report forms with urine toxicology will occur as well as recording of concomitant medications and adverse events. Neurocognitive testing will be completed on Baseline 1, Baseline 2 and Week 8. Where indicated, participants will be administered the neurocognitive tests and the scanning sequence of the MRS will be completed based on scanner availability and at the discretion of the PI or PI's designee. Subject will be read MRI instructions 48hrs prior to Baseline 1, Week 1, and Week 8 visits to have the subject avoid specific foods, medications, alcohol and cigarettes starting 24hrs prior to the MRS scan. A light lunch/snack may be provided after the fasting lab work.

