**+ - for patients with a CRP>3mg/L and a Single Item Screening Scale for Fatigue Score ≥4**

**\* - for patients completing the main branch of the Riluzole Study**

**\*\* - for patients who opt for to complete the Startle Test Study**

**Key:**

**Main Riluzole Study**

\*Screening/ Safety Labs: CBC w/Diff, Metabolic Panel, hCG quantitative serum, TSH, Urinalysis w/micro at Screening and Week 8 only, Urine drug test all visits (test kit), except week 2 visit; Testing for CRP, Hepatitis B and C and HIV will be conducted on the screening visit only, unless otherwise approved by the PI. A Rapid C Reactive Protein finger prick may also be obtained by trained research staff using a rapid CRP finger prick test at the discretion of the investigator to expedite determining eligibility for research participation.

\*Psychiatric Assessments: WRAT-3, MMSE, CTQ, QID-S, Single Item Screening Scale for Fatigue

\*Research Blood: Cytokine Multiplex, TRP, KYN, mRNA analysis, methylation analysis, and gene analysis (collected under fasting conditions)

\*Self-Report Forms: IDS-SR, MFI, PROMIS-Fatigue, BAI, PSQI, Assessment of Pain level, PHQ-9, Single Item Screening Scale for Fatigue, Baycrest Memory Scale

\*Neurocognitive Tests:

Baseline 1 - EEfRT, Finger Tapping Task (FTT), The Trail Making Test (TMT), Digit Symbol Task, Reaction Time Task (CANTAB)

Baseline 2 - Rey Auditory Verbal Learning Test (RAVLT), Delayed Matching To Sample (CANTAB), Spatial Working Memory (CANTAB), Stroop Color and Word Test

Week 8- EEfRT, Finger Tapping Task (FTT), The Trail Making Test (TMT), Digit Symbol Task, Reaction Time Task (CANTAB), Rey Auditory Verbal Learning Test (RAVLT), Delayed Matching To Sample (CANTAB), Spatial Working Memory (CANTAB), Stroop Color and Word Test

[figure not shown]

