## **Week 8:**

Subjects will complete all neurocognitive testing from baseline 1 and baseline 2. Testing will be divided into two sessions with a break of at least ½ -1 hour.

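### Aim 2: the scheduled cognitive tests and EEfRT give one change score per woman, so a random-intercept model of change has confounded variance components; a regression of the Week 8 score should replace it

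*Combined protocol and SAP*

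**What the plan says.** Section 10 (Statistical Analysis), Aim 2, gives one model type for all behavioural outcomes: "Random intercept linear mixed models will be used to assess whether change in left or right basal ganglia or dACC glutamate predict change". The outcome is described as "change in fatigue scores or change in neurocognitive function over time". The tests are not pooled: "Separate analyses will be run for each behavioral outcome (MFI, PROMIS) as well tests of cognition". The section does not say whether the response is a computed difference or the score at each visit, or how many rows each woman contributes.

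Description of Study Procedures says: "Neurocognitive testing will be completed on Baseline 1, Baseline 2 and Week 8". That suggests three scores per test, but the key to Table 1 divides the battery:

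- Baseline 1: EEfRT, Finger Tapping, Trail Making, Digit Symbol and Reaction Time.
- Baseline 2: "Baseline 2 - Rey Auditory Verbal Learning Test (RAVLT), Delayed Matching To Sample (CANTAB), Spatial Working Memory (CANTAB), Stroop Color and Word Test".
- Week 8: both sets. The Week 8 paragraph under Neurocognitive Tests confirms this: "Subjects will complete all neurocognitive testing from baseline 1 and baseline 2".

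MRS is done at Baseline 1, Week 1 and Week 8. Table 1 marks the self-report forms, which include MFI and PROMIS-Fatigue, at both baselines and at Weeks 1, 2, 4 and 8.

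**The concern.** A random intercept separates variation between women from variation within a woman, so it needs at least two rows per woman. A test scored once before treatment and once after gives a single difference. If that difference is the response, nothing in the data can divide the total variance between the intercept and the residual. Software may refuse the model or return an arbitrary split, and the reported standard error may then be wrong without warning.

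At stake are the p-values for the processing-speed, executive-function and motivation parts of Hypothesis 2, and for memory if the scheduled memory tests are analysed. These p-values feed the step-down Bonferroni procedure in Section 10, so one unreliable value can affect the decisions on others. Aim 1, on which the sample size rests, is not affected.

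**Working it through.** The plan gives no figure on this point to reproduce. The check counts rows and then tests what can be estimated.

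**1. Rows per woman** (Table 1, its key and the Week 8 paragraph)

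| Outcome | Before treatment | On treatment, paired with MRS | Change scores paired with MRS |
|---|---|---|---|
| TMT, FTT, Reaction Time, Digit Symbol, EEfRT | 1 (Baseline 1) | 1 (Week 8) | 1 |
| RAVLT, Delayed Matching, Spatial Working Memory, Stroop | 1 (Baseline 2) | 1 (Week 8) | 1 |
| MFI, PROMIS-Fatigue | 2 (both baselines) | 2 (Weeks 1 and 8) | 2 |

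With 40 women, each cognitive test or EEfRT gives 40 change scores.

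**2. Response = change score.** For woman *i*, D_i = a + c·G_i + u_i + e_i, where G_i is glutamate change. With one row each, Var(D_i | G_i) = τ² + σ², and women are independent. The likelihood depends only on the sum τ² + σ². This is algebra and does not depend on any simulated value.

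An illustration with n = 40 (slope and variances assumed) gave these REML log-likelihoods by intercept share of the total variance:

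| Share | 0 | 0.25 | 0.50 | 0.75 | 0.95 |
|---|---|---|---|---|---|
| One change score | −12.688 | −12.688 | −12.688 | −12.688 | −12.688 |
| Two visit scores | −44.49 | −38.73 | −34.02 | −32.19 | −93.70 |
| Two change scores (as for fatigue) | −56.94 | −52.20 | −48.27 | −47.28 | −111.67 |

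The rows come from different responses, so only the shape within a row is informative. The first row is flat. The other two have an interior maximum, so those models are identified.

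**3. The slope.** With one change score per woman, the slope was −0.3723 at every split, the same as ordinary regression (SE 0.1309, 40 − 2 = 38 residual df). The model of the two visit scores (80 rows, time × glutamate change, random intercept) gave −0.3723 with SE 0.1309.

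**4. The standard error in practice.** A correct calculation uses only τ² + σ² and returns the ordinary regression SE. One mixed-model routine (Python statsmodels) usually did so. From one start value, however, it returned 0.021 against 0.131 from ordinary regression, and the likelihood gave no sign of a problem.

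**5. Using the pre-treatment score as a covariate.** Assume equal variance s² before and after treatment, pre-post correlation ρ, and no correlation between the pre-treatment score and glutamate change. Then:

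- variance of the change score = 2s²(1 − ρ)
- residual variance after adjusting for the pre-treatment score = s²(1 − ρ²)
- ratio = (1 − ρ²) / [2(1 − ρ)] = (1 + ρ)/2

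The ratio is 0.75 at ρ = 0.5, 0.85 at 0.7 and 0.90 at 0.8. The corresponding SE ratios are √0.75 = 0.87, √0.85 = 0.92 and √0.90 = 0.95. Simulated SEs agree: 0.139 against 0.158 at ρ = 0.5 (ratio 0.88), and 0.114 against 0.122 at ρ = 0.7 (ratio 0.93). The documents do not give ρ, so these values are assumptions.

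**The case against.** A reader might infer that the Aim 2 model cannot be identified at all, or that Hypothesis 2 cannot be tested for cognition. The documents do not support that, for two reasons.

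First, even with change as the response, only the split of two nuisance variances is lost. The glutamate slope, which is what Aim 2 asks about, is identified and equals the ordinary regression slope.

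Second, Section 10 does not say that a difference is the response. Its reference to change over time also fits a model of the two visit scores with a time by glutamate-change term, and a random intercept has a purpose there. That model is identified and reproduces the regression of change on change. This part of the objection stands. What remains is that Section 10 does not specify that model, and other visit-level forms are not equivalent. Entering glutamate as a time-varying predictor mixes between-woman and within-woman associations. In a simulation with a true within-woman slope of 0.30 and an assumed between-woman association, that form averaged 0.37, while change on change averaged 0.29.

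The SE of 0.021 comes from one package at one setting. Section 9 names SPSS, SAS, Stata and R as export targets, and none of these was tested. The example shows that an SE can be wrong; it does not give a typical size.

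Change-score analysis is not an error in itself. Glutamate change is observed and not randomised, so adjusting for the pre-treatment score can also alter the quantity estimated. In least squares, the change-on-change slope equals the adjusted slope plus (b − 1)·d, where b is the coefficient of the pre-treatment score and d is the slope of that score on glutamate change. The two agree when d is near 0 or b is near 1.

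The point cannot extend to every test in Section 10. HVLT-R, PASAT, COWAT, DDT and five further motivation tasks are absent from the schedule, so their scores cannot be counted. EEfRT is the only scheduled motivation task.

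**Conclusion.** The point holds within limits. It covers the tests both named in Section 10 and scheduled (Trail Making, Finger Tapping, Reaction Time, Digit Symbol and EEfRT), and the other scheduled tests (RAVLT, Delayed Matching, Spatial Working Memory and Stroop) if they are analysed. On the most literal reading, the random-intercept model of change has confounded variances and may give an unreliable SE and p-value, while the slope is sound. On the alternative visit-level reading with time by glutamate change, the model is identified but amounts to a change-score analysis. On both readings the pre-treatment score can be put to better use, and the response needs to be stated.

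The likely precision gain is modest: an SE roughly 12% lower at ρ = 0.5 (1 − 0.139/0.158) and 7% lower at ρ = 0.7 (1 − 0.114/0.122), under the assumptions in the check. There is little or no gain if the test is very stable or its pre-treatment score correlates with glutamate change. The row count assumes that Baseline 2 testing precedes the first dose, as its baseline label implies. MFI and PROMIS are unaffected, because Weeks 1 and 8 both pair with MRS.

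**What to change.** In Section 10, Aim 2, state the response variable and the rows per woman for each outcome. For the scheduled tests with one pre-treatment and one Week 8 score, replace the random-intercept model with one linear regression per test and brain region. Regress the Week 8 score on the same test's pre-treatment score and the Baseline 1 to Week 8 glutamate change, with the clinical covariates that the section already calls for. Keep the random-intercept model for MFI and PROMIS.

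Do not add treatment arm to the main model without saying so. It removes the between-arm part of glutamate change and turns the question into a within-arm association, so it belongs in a sensitivity analysis.

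The cost is one sentence in Section 10 and one residual degree of freedom per model (40 − 3 = 37 in place of 38, before other covariates). No new data are needed for the scheduled tests. Tests named in Section 10 but not scheduled need a separate decision, which this change does not settle.
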